individuals tolerate heat-denatured food proteins more easily than raw proteins. Moreover, the potential use of heat-denatured food proteins to speed up tolerance towards allergens has recently been suggested. Hence, the hypothesis was generated that ingestion of small amounts of denatured proteins might lead to higher rates of tolerance induction (11). We were able to demonstrate the change in food protein components upon heating of hen's egg allergen in specific recipes, and furthermore reported that by gradual introduction of progressively less heated hen's egg containing products, tolerance in infants was observed after 24-30 weeks in baked-egg tolerant subjects (12). In parallel, heat inactivation of cow's milk proteins has also been reported (13) and results in gradual tolerance in cow's milk allergic subjects (14). Moreover, the psychological impact of introduction of some heat denatured food proteins in the diet of children with strict allergen avoidance, has been demonstrated to be of utmost importance (15). In pedEoE however, the effect of heat denaturation on the eosinophilic inflammation in the esophagus, has not yet been studied. We have several indications that allow us to hypothesize that heat denaturation in pedEoE could allow protein introduction while allowing remission rates, as observed in typical IgE-mediated food allergy. Indeed, pediatric EoE (pedEoE) (in contrast to EoE in adults) is linked in over 80% of cases to IgE mediated food and/or environmental allergy (PhD thesis [name], Manama thesis [name]). Moreover, the same short list of 6 food products as described in food allergy, namely milk, hen's egg, wheat, soy, peanut/tree nuts, fish/shellfish is involved in more than 60% of the pedEoE cases (10). In an almost similar percentage (58%) when compared to 6-food diet, remission in pedEoE patients is possible using an allergy-test directed elimination diet (10) also pointing to involvement of IgE mediated allergy in pedEoE (2). Moreover, allergen oral immunotherapy protocols in IgE mediated food allergic patients on the opposite, can induce pedEoE in small numbers between 0.5-1% (16). We furthermore demonstrated in a patient with eosinophilic gastro-enteritis that plant-food pollen-associated eosinophilic increase can be the driving force of the disease (17). All of these point to the involvement of IgE mediated allergy in pedEoE opposed to EoE in adults. Finally, recently a report in a boy with cow's milk protein induced EoE, demonstrated that heat-denaturation of the cow's milk proteins induced remission, in a cow's milk driven pedEoE (18). We therefore will study, similarly as in children with IgE mediated food allergy, the possibility to introduce heat-denatured cow's milk or hen's egg protein instead of complete avoidance in order to induce remission in pedEoE. To that aim, we intend to provoke 8 pedEoE children on a hen's egg and/or cow's milk free diet, with heat denatured hen's egg and/or cow's milk proteins and plan a biopsy to study remission after 8 weeks of introduction at home. If the (re)introduction

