
was successful, we will introduce recipes with gradually less heated proteins after which sequentially a new biopsy will be performed after 8 weeks of introduction. Although it can be anticipated that introduction of the least heated step (raw egg and/or uncooked (UHT-)treated cow's milk) will induce recidive of the disease, we will discuss with parents whether or not they would accept an 8-weeks reintroduction protocol of the final step and afterwards observation of its effect on the esophagus in their children. One might indeed even hope for tolerance induction while using this graded protocol, similar as in food protein allergic subjects, although we have no indication of such a tolerance induction in EoE patients, who today are taught to avoid these allergens "live-long".

In contrast to the results related to allergen sIgE, allergen-specific IgG4 (sIgG4) is more consistently associated with oral tolerance (18bis). Allergen sIgG4 antibodies can compete with IgE for allergen binding to type II IgE receptor-expressing cells, such as basophils and mast cells, leading to the blockage of this receptor. The production of both IgE and IgG4 antibodies is known to be up-regulated by interleukin-4 (IL-4) produced from activated Th2 cells. However, IL-10 secreted by Treg cells can suppress IgE production and simultaneously increase IgG4 production (Figure 5). Therefore, IgE and IgG4 production are not always similarly increased. Not only are IgE and IgG4 important to predict reactivity to an allergen or to confirm food tolerance, also the ratio of IgE to IgG4 seems to play a key role (19).

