The objective of the study is to study whether the introduction of heated food products (more specifically heated hen's egg and/or cow's milk) in children with EoE would be possible without re-occurrence of the eosinophilic inflammation, while the intake of less heated products might cause disease recidive. Moreover, we would like to study whether the gradual re-introduction of less heated products after the most heated form is tolerated, could lead to tolerance induction in EoE.

Primary end-point:

- Primary end-point of the study is to study the number of ped EoE children by inclusion on hen's egg and/or cow's milk free diet with potential remaining remission (<15 eosinophils/hpf on esophageal biopsies) after 8 weeks (re)introduction of heat-denatured hen's egg and/or cow's milk proteins (introduced sequentially as on the one hand baked egg (cake), hard-boiled egg, omelet and soft-boiled egg and on the other hand 20' cooked cow's milk, 15', 10' and 5' cooked cow's milk).

Secondary end-points:

- The number of pedEoE children in whom remission remain with introduction of cake and/or 20'cooked cow's milk (step 1), but no longer with less heated proteins
- To study whether remission is associated with specific circulating and/or local food protein IgG4 reduction (when baseline levels (serum) would be (stored) available) (and increase upon unsuccessful introduction of less heated proteins)
- To study whether remission could be associated with changes in local IgG4 production (on biopsy staining)
- To study whether we could develop an *in vitro* mimicking B cell activation test by stimulating PBMC with food proteins obtained after different heat-denaturating steps
- Can we observe a correlation between Pediatric EoE PEES v2.0 and Peds-QL scores (obtained in all ped EoE children participating in study s64441) and histologic remission?
- To study the presence of associated atopy (tree-, grass- or weed pollen or fungi allergy)
- To study the presence of associated typical IgE mediated food allergy (sensitization and documented symptoms)

Material and methods

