- *Inclusion criterion:* All children (aged 12 months and older) presenting (since 1-1-2014: moment of diagnostic guideline standardization for pedEoE) with diagnosed pedEoE at UZ Leuven eliminating either hen's egg or cow's milk or both and in complete remission after their latest biopsy (no longer than 12 months earlier, but preferentially as short as possible after their latest biopsy) are eligible for the study. If the last biopsy has been performed more than 12 months earlier, a new gastro-duodenoscopy will be performed to verify remission and rule out e.g. active gastritis. If they are on PPI and/or local budesonide treatment, this should be stable for at least 3 months and will remain untouched during the entire study. We will include 18 pedEoE subjects in total.
- *Exclusion criteria:*
 - Children younger than 12 months
 - Children with active pedEoE
 - Children who refuse to adhere to the protocol
 - Children with associated IgE mediated hen's egg and/or cow's milk allergy with specific IgE antibody titers that predict active (baked egg and/or baked milk) food allergy with cut-off titers as used at the consultation of allergy (KLL). Those children will become eligible however if their titers decrease while the study is still open.

Study design:

Study subjects and study procedure

If inclusion criteria are met, after obtaining informed consent from the parents (and when old enough, assent from the children) 18 children will be included in this pilot pedEoE trial.

Children will be provoked in-house (UZ Leuven petit-cru), based on the written procedure available for heated egg (wheat or rice flour based) or cow's milk provocation. If on diet for both, parents and children will decide which allergen they will start with, but both food products will be introduced sequentially in time (this is after complete termination of the first food introduction). Afterwards, they will introduce heated egg by cake or 20' boiled cow's milk at least three times a week for 8 weeks (as for the TETI study (10)) and will return to the hospital for a gastroscopy with biopsies. EoE remission will be studied on 2X3 biopsies

(upper and lower esophagus) by eosinophil staining within the routine anatomopathological laboratory within our hospital.

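### The eosinophil count behind the primary end-point, step progression and the stopping rule has no provision to mask its reader to food or heating step

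*Protocol*

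**What the plan says.** The primary end-point (Protocol, Study objectives) is the number of children "with potential remaining remission (<15 eosinophils/hpf on esophageal biopsies) after 8 weeks" of introduction. It covers four heating steps for egg and four for milk.

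On the reading itself, Study subjects and study procedure says "EoE remission will be studied on 2X3 biopsies", taken from the upper and lower esophagus and examined "by eosinophil staining within the routine anatomopathological laboratory within our hospital". The protocol says nothing more about who reads, what the reader is told, or whether the deciding figure is a peak or a mean.

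The same reading has three further uses:
- It decides progression. The visit schedule ties a go/no-go call to the biopsy result after steps 1 and 2, and the study procedure makes later steps conditional on continued remission.
- It feeds the first secondary end-point: children who stay in remission at step 1 but not with less heated protein.
- It drives the stopping rule under Statistical analysis, which applies if all 18 children relapse at step 1.

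The study is a single group: "18 children will be included in this pilot pedEoE trial". Food and step are known to families and staff. For a child avoiding both foods, "parents and children will decide which allergen they will start with". Recurrent symptoms bring the gastroscopy forward.

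**The concern.** A threshold applied to a count from selected microscope fields on six biopsies leaves some room for judgement when the count lies close to 15. If the reader knows that a sample comes from the most heated step, or from a less heated one, that room can be used, without intent, in the direction the study expects.

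The protocol states such a direction. Its objective is to see whether heated egg or milk can be introduced without the inflammation returning, while less heated forms might bring it back. A tilt that followed this expectation would raise the remission count at step 1 and lower it later, which is the pattern counted by the first secondary end-point. There is no comparator arm in which the same tilt could cancel.

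The plan for descriptive reporting without testing does not remove the problem, because the reported number of children is itself what would shift. Nor can an analysis plan repair it later: what the reader knows has to be settled before the slides are read.

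**Working it through.** The protocol gives no misreading rate, no share of biopsies expected near the cut and no derivation of the sample size. There is therefore no figure of the plan to reproduce. The check sets the statements side by side and then asks how much depends on one reading.

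**1. What is fixed and what is not**

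| Element | Protocol |
|---|---|
| Deciding measure | Eosinophils/hpf, cut at 15 (Primary end-point) |
| Material | 2 × 3 biopsies, upper and lower (Study procedure) |
| Place of reading | Routine pathology, same hospital (Study procedure) |
| Reader's knowledge of food, step, symptoms | Not addressed |
| Coded samples, second reading, peak or mean | Not addressed |
| IgG4 stain on the same biopsies | Reader assigned; masking not addressed (Blood and esophagus biomarker study) |
| Comparator | None described |
| Expected direction | Heated tolerated, less heated may relapse (Study objectives) |

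**2. Leverage of one reading on the primary count**

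With n = 18, one reclassified child moves the proportion by 1/18 = 5.6 percentage points. The Introduction gives a different number: "we intend to provoke 8 pedEoE children on a hen's egg and/or cow's milk free diet". With n = 8 the step is 1/8 = 12.5 points. The two sample sizes must be reconciled; the figures below use 18.

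**3. Leverage of one reading on the stopping rule**

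The rule needs relapse in 18 of 18, so a single relapse read as below 15 prevents it from applying. Suppose all 18 truly relapse at step 1 and each relapse is independently read as remission with probability f. The protocol gives no f; 2% to 20% is an assumed range.

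P(rule applies) = (1 − f)^18

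| f (assumed) | P(rule applies) | P(at least one false remission) |
|---|---|---|
| 2% | 69.5% | 30.5% |
| 5% | 39.7% | 60.3% |
| 10% | 15.0% | 85.0% |
| 20% | 1.8% | 98.2% |

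This shows how sensitive the rule is to misreading of any kind. It does not measure the gain from masking, which would remove only the part of f caused by expectation and leave random counting and sampling error as they are.

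**4. Why no number of biased readings is given**

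Such a number needs the share of biopsies near 15, the share of those whose true count lies on the unexpected side, and the chance that knowledge of the step tips the reading. None is in the protocol. The middle quantity matters: a near-cut biopsy already on the expected side cannot be moved there.

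**The case against.** The strongest reply is that the protocol states nothing wrong. It does not say that readers know the food or step, and it describes no request form. A cell count against a numeric cut, on a fixed set of biopsies, in a routine laboratory that may be separate from the trial team, is a fairly objective measure. The study is a descriptive pilot. Withholding information from a pathologist whose report steers the child's care is also more than clerical.

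Much of this stands. A reader might infer that the slides are read with full knowledge of food, step and symptoms. That rests on the protocol's silence and on ordinary practice with routine requests, not on its text.

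A reader might also cite the Introduction, where relapse is anticipated at the least heated step, as proof of a strong expectation. That remark concerns raw egg and uncooked UHT milk, the optional step after step 4 and outside the primary end-point. The same part of the Introduction hopes for tolerance. For the primary steps the weaker wording of the objective is the proper basis.

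Nor is masking the sole safeguard: a second reading, a stated counting rule and recorded numeric counts would each help.

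What remains is that one reading carries the end-point, progression and stopping, in a one-group study with a stated expectation, and the plan makes no provision for the reader's independence from it.

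**Conclusion.** The point holds as a cheap improvement to conduct, not as an error in the protocol. The plan leaves open a risk of reading bias near 15 eosinophils/hpf in the measure on which most else depends.

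The size of that bias cannot be derived from the documents. What can be stated is the leverage: 5.6 percentage points per child with 18 children, and a stopping rule that one reading can prevent from applying. A reader might go further and attach a number of misclassified children to the lack of masking; the documents do not support any such figure.

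The conclusion assumes that the routine reader could learn the food or step from the request or the record. If the laboratory already reads without that information, a sentence in the protocol saying so settles the masking question.

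**What to change.** Amend the study procedure and the biomarker section as follows:

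1. Submit study biopsies under a study code with only 'EoE follow-up' and upper or lower esophagus. The code should not carry the visit number, because the visit schedule links visits to steps.
2. Withhold food, step and study-related symptom information from the eosinophil reader and the IgG4 reader until the count is signed. Then release it for the clinical report, so that the go/no-go call can proceed on the full report.
3. Record the peak eosinophils/hpf for each level as a number, and report these counts beside the yes/no result. Readers can then see how many results lie close to 15. They can also see how many fall in the 5 to 15 band, which the Introduction's account of treatment guidelines classes as partial remission while the primary end-point counts results below 15 as remission.

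The cost is a changed request form and a two-stage sign-off. Children, visits, slides, laboratory and reader stay the same. The real downside is that the pathologist has less clinical context until the count is signed; releasing the information at that point limits it.

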1.1. Adverse Event (AE)

An AE is any untoward medical occurrence in a patient or subject during an experiment, and which does not necessarily have a causal relationship with this treatment.

An AE can therefore be any unfavourable and unintended sign (including an abnormal laboratory finding), symptom or disease temporally associated with the use of a product, whether or not considered related to the product. Any worsening (i.e., any clinically significant adverse change in the frequency or intensity of a pre-existing condition) should be considered an AE.

1.2 Adverse Reaction (AR)

An AR is any untoward and unintended responses to an investigational medicinal product or to an experiment and, when an investigational product is concerned, related to any dose administered.

1.3 Serious Adverse Event (SAE)

An SAE is any untoward medical occurrence that results in any of the following:

- Death
- A life-threatening^a experience
- In-patient hospitalisation or prolongation of existing hospitalisation
- A persistent or significant disability or incapacity
- A congenital anomaly or birth defect
- Important medical events that may be considered an SAE when - based on appropriate medical judgement - they may jeopardise the subject and may require medical or surgical intervention to prevent one of the above outcomes

^a The term “life threatening” in the definition of SAE refers to an event in which the subject was at risk of death at the time of the event. It does not refer to an event which hypothetically might have caused death if it was more severe.

1.4 Adverse Events of Special Interest (AESI)

Define here any AEs that are of special interest (e.g. specific for the intervention) and must follow the same reporting timelines as SAEs.

The following events should be reported within the same timelines as SAEs:

- none

2 Adverse Events that do not require reporting

Define here any AEs or SAEs that are expected and do not require reporting for this trial. The following should not be reported as AEs:

- Pre-existing conditions, including those found as a result of screening (these should be reported as medical history or concomitant illness).
- Pre-planned procedures unless the condition for which the procedure was planned has worsened from the first trial-related activity after the subject has signed the informed consent.

The following events are commonly observed in the study population and are therefore not considered as adverse events for the purpose of the trial:

- (seasonal) allergic rhinoconjunctivitis, (seasonal) asthma attacks, atopic dermatitis

Although these events should not be reported to the Sponsor, these should be recorded in the patient's medical notes according to routine practice.

The following events not to be considered as SAEs are:

- Pre-planned hospitalisations unless the condition for which the hospitalisation was planned has worsened from the first trial-related activity after the subject has signed the informed consent.
- Hospitalisation as part of a standard procedure for protocol therapy administration. However, hospitalisation or prolonged hospitalisation for a complication of therapy administration will be reported as an SAE.
- Hospitalisation or prolongation of hospitalisation for technical, practical, or social reasons, in absence of an AE.

3 Recording and reporting of Adverse Events

See also: Safety Reporting ; Documents.

The information listed below that should be recorded for each AE can be supplemented with additional information. These data points should be incorporated in the (e)CRF.

Specific timelines for reporting AEs in the (e)CRF can be added, e.g. within 7 days after becoming aware.

Investigators will seek information on AEs during each patient contact. All events, whether reported by the patient or noted by trial staff, will be recorded in the patient's medical record and in the (e)CRF within a reasonable time after becoming aware. If available, the diagnosis should be reported on the AE page, rather than the individual signs or symptoms. If no diagnosis is available, the Investigator should record each sign and symptom as individual AEs.

The following minimum information should be recorded for each AE:

- AE description
- start and stop date of the AE
- severity
- seriousness
- causality assessment to the study interventions
- outcome

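### The AE exemption for three atopic diagnoses has no limit for worsening or a suspected food link, so non-serious flares provoked by study food can go unreported

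*Protocol*

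**What the plan says.** The protocol's Adverse Event Reporting chapter treats these events in several places.

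- **Section 1.1 (definition).** An AE is any untoward occurrence, related or not, and a change for the worse counts: "Any worsening (i.e., any clinically significant adverse change in the frequency or intensity of a pre-existing condition) should be considered an AE".
- **Section 2 (events that need no reporting).** Three diagnoses are declared not to be AEs in this trial because they are common in the population: "seasonal) allergic rhinoconjunctivitis, (seasonal) asthma attacks, atopic dermatitis". The next sentence begins "Although these events should not be reported to the Sponsor" and asks for a routine entry in the medical notes.
- **Section 2, neighbouring items.** Most carry a limit. Two have a worsening clause: "Pre-planned procedures unless the condition for which the procedure was planned has worsened" and "Pre-planned hospitalisations unless the condition for which the hospitalisation was planned has worsened". A third keeps complications reportable: "hospitalisation or prolonged hospitalisation for a complication of therapy administration will be reported as an SAE". A fourth applies only "for technical, practical, or social reasons, in absence of an AE".
- **Section 3 (recording).** All events are to go into both the medical record and the (e)CRF, and where a diagnosis is available "the diagnosis should be reported on the AE page, rather than the individual signs or symptoms".
- **Section 3.1 (assessment).** Seriousness, severity and causality are evaluated for AEs.
- **Section 1.4.** No adverse events of special interest are named.

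**The concern.** The intervention is re-exposure to egg or milk, and the introduction to the protocol links paediatric EoE to IgE-mediated food and/or environmental allergy in over 80% of cases. Eczema, asthma and rhinoconjunctivitis are part of these children's background, but a flare of one of them could also be a reaction to the study food. The stated reason for the exemption covers the background. It does not cover a flare that is worse than usual or that the investigator suspects the food has provoked, yet the wording exempts both.

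At stake is the safety description of an 18-child pilot that will be reported mainly descriptively. If food-provoked flares are filed under an exempted diagnosis, the AE data sent to the Sponsor will understate them, and nobody is required to judge whether the food was the cause.

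**Working it through.** No arithmetic applies to the core of this point, and the plan gives no figure to reproduce. The check is to follow one case through the sections.

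**Case.** A child has mild, stable atopic dermatitis at entry. During a home introduction step the eczema becomes clearly more frequent and more intense. No seriousness criterion is met.

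1. Section 1.1: clinically significant worsening of a pre-existing condition, so it is an AE.
2. Section 2: the diagnosis is on the exempt list, so it is not an AE and is not reported to the Sponsor. Nothing in the item asks whether the episode is worse than usual or possibly food-related.
3. Section 3: all events go to the medical record and the (e)CRF, whereas section 2 mentions only the medical notes. Because the diagnosis is preferred to signs and symptoms, the flare is likely to be labelled with the exempted term.
4. Section 3.1: causality is assessed for AEs. An event already ruled not to be an AE need not reach this step.
5. Sections 1.2 and 4.1: the adverse reaction definition and the yearly overview of SARs are not narrowed by section 2, but they help only once a link to the food has been recognised, which is the judgement that step 4 can skip.

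So the same event is an AE under one section and not under another, and the route that drops it does so before causality is considered.

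**Does the bracketed word repair this?** No. It may or may not confine the first two diagnoses to seasonal episodes, and atopic dermatitis carries no qualifier at all.

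**Could such flares occur in this trial?** The documents make it plausible, without giving a rate.

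- The allergy exclusion concerns IgE titres that predict active baked egg or baked milk allergy.
- The introduction says that allergic individuals tolerate heated protein more easily than raw. Tolerating step 1 therefore does not rule out a reaction at a less heated step.
- The visit list shows 4 required steps. One starts with an in-hospital provocation (V1). The other 4 − 1 = 3 start with a clinical examination and dietary advice (V3, V5, V7).

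**The case against.** The strongest reply is that section 2 is a deliberate, trial-specific exemption, and a specific rule may narrow a general definition. That stands as a principle, so the problem is better described as an exemption drawn wider than its own reason than as a flat contradiction. The reason supports exempting episodes at their usual level and nothing more.

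Other parts of the reply also have weight.

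- **The information is not lost.** Section 2 keeps the events in the medical notes, and it does not expressly forbid an (e)CRF entry, which section 3 asks for. A reader might infer that these flares disappear altogether. The documents do not support that. What can be lost is the report to the Sponsor and the causality assessment.
- **Serious events.** A reader might infer that a hospitalised asthma attack is exempt too. That is not the natural reading: section 1.3 defines an SAE as any untoward occurrence meeting a listed criterion, and the separate list in section 2 of what is not an SAE does not name these diagnoses.
- **The neighbouring items are a weak comparison.** The four with limits concern procedures and hospitalisations. They show that the authors knew how to write a worsening clause, but the argument does not depend on them.
- **Symptom surveillance exists.** The study procedure puts a step on hold and brings the gastroscopy forward if symptoms recur. This probably means EoE symptoms. In any case it adds no AE record and no causality assessment for an atopic flare.

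None of these returns a worsened or food-related non-serious flare to the AE data reported to the Sponsor.

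**Conclusion.** The point holds in a limited form. As written, section 2 lets non-serious flares of three atopic diagnoses be left out of Sponsor-reported AE data without a causality assessment, even when they are worse than the child's usual state or suspected to come from the study food. This goes beyond the reason given for the exemption and does not fit sections 1.1 and 3.

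Its size cannot be put as a number. The protocol gives no flare rate. The figure of over 80% describes allergy of any food or environmental kind, not these three diagnoses, and the exclusion criteria remove some allergic children, so it cannot be turned into a count of missed events. Reactions outside the three diagnoses, such as urticaria, vomiting or anaphylaxis, are not exempted. The primary end-point is histological and is unaffected.

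The conclusion assumes that sites apply section 2 as it reads. A site that follows sections 1.1 and 3 instead would capture the flares, and two such sets of records would not be comparable. The change is worth making before data are collected, but the point does not threaten the trial's main result.

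**What to change.** Reconcile section 2 with sections 1.1 and 3:

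- Limit the exemption to non-serious episodes of the three diagnoses that are at the child's usual, pre-study frequency and severity and that the investigator does not suspect are related to the study food or a study procedure.
- Record every other episode as an AE, with causality assessed under section 3.1.
- Note each child's usual atopic symptoms at V0 or V1, so that worsening can be judged against something.
- State whether the bracketed word seasonal restricts the first two diagnoses.

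The test should be suspected relation, not timing alone. Study food is eaten at least three times a week in step 1 and two to three times a week in step 2, so almost any episode would fall close to an intake and a timing test would nearly cancel the exemption.

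The cost is a few sentences in section 2 and one baseline note per child. The downside is a few more AE entries, some of which will turn out to be background atopy.
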